12.4.3 Cost of Healthcare Utilization

To collect healthcare utilization data a questionnaire similar to the ACTG Instrument named “ACTG A5265 Resource Utilization Interview” will be used following minor adaptation for A5360.

Staff will administer this instrument at the entry visit, the week 24/SVR evaluation visit, at the weeks 48 and 72 planned study visits, and at any unplanned study visit.

To translate utilization to cost, we will use WHO CHOICE estimates of the cost of health care delivery (clinic visits, hospital nights, casualty ward visits) by country.

12.5 Assessing SVR Status

See section 10.2.1 for primary outcome measures. Sensitivity analyses will explore cases where non-SVR inferred due to LTFU.

12.6 Estimation of Cost/SVR Outcome

- 12.6.1 Program perspective. We will estimate the mean cost per participant including:
 - Cost of medications
 - Cost of all planned and unplanned study visits between weeks 0 and 24/SVR evaluation including staff time and laboratory tests

- 12.6.2 Healthcare sector perspective
 - Cost of medications
 - Cost of all planned and unplanned study visits between weeks 0 and 24/SVR evaluation including staff time and laboratory tests
 - Cost of healthcare utilization between weeks 0 and 24/SVR evaluation
 - The DIFFERENCE in healthcare utilization as measured at weeks 0 and 48

Cost/SVR attained in each country will be calculated, as well as for the entire study population. Cost/SVR both in local currency and in international dollars will be stated. The cost/participant who does NOT attain SVR will also be estimated. Sensitivity analyses will demonstrate the impact of HCV therapy costs on the cost-benefit of MINMON.

In addition, although there is no control arm to which we can compare the cost/SVR attained in MINMON, we will estimate the cost/SVR attained for the standard of care treatment protocol based on the cost of laboratory tests and medications and the planned schedule of events for a standard of care treatment course.

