3.0 STUDY DESIGN

This study will enroll 400 participants who will be followed using a MINMON protocol for a duration of 24 weeks in order to obtain primary outcome information regarding SVR status, as well as additional information for secondary objectives over the longer duration of 72 weeks. The MINMON strategy is comprised of: 1) minimal pre-treatment assessment including confirmation of viremia by HCV RNA and liver disease staging using routine clinical exam and non-invasive parameters (ALT, AST, and platelet count [and bilirubin, albumin, and INR in persons with evidence of cirrhosis by FIB-4]) and no genotyping; 2) distribution of complete HCV treatment course at study initiation (i.e., 84 days of SOF/VEL); 3) no planned on-treatment laboratory monitoring; 4) no planned clinic or pharmacy visits prior to SVR evaluation; and 5) remote contact at treatment week 4 and post-treatment at week 22 to update locator information and to facilitate attendance at the SVR evaluation visit (weeks 22 to 28). The week 4 remote contact will include adherence assessment and reinforcement which is also considered to be a part of the MINMON strategy.

All participants will be treatment-naïve, with active HCV-infection, with or without HIV-1 co-infection, and if cirrhotic, will be classified as compensated cirrhotics based on CTP score. All participants will receive study-provided treatment (FDC of SOF/VEL) for a duration of 12 weeks followed by evaluation 12 weeks later to ascertain SVR status. Upon SVR evaluation, all participants will enter Step 2 of the study and will be followed for an additional 48 weeks to examine liver disease regression post-SVR, measure the incidence of HCV re-infection, and other non-primary outcomes. Measures of disease regression after cure are important to understanding future disease burden and cost associated with liver disease. Reinfection rates are critically important for both public health planning and advocacy purposes when seeking to expand the availability of HCV treatments. In addition, cost-benefit analyses will be conducted using cost data and outcomes gathered from this study.

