6.0 CLINICAL AND LABORATORY EVALUATIONS

6.1 Schedule of Evaluations

6.1-1: Schedule of Evaluations: Step 1- Visits up Until SVR Evaluation

Evaluation	Screening	Entry/Week 0	Weeks			SVR Evaluation Visit (if week 24 visit is missed; can occur up to week 72)	Unplanned Study Visits (see section 6.2.6)
			4	22	24		
			Window \pm 7 days		Window -14/+28 days		
Documentation of Active HCV Infection	X						
Documentation of HIV-1 Status	X						
Calculated FIB-4 Score	X				X	X	As needed.
MELD Score		X					
Documentation of Cirrhosis Status	X				X	X	As needed.
Calculated CTP Score (if cirrhotic by FIB-4)	X				X	X	
Liver Elastography (see section 6.3.7)		X			X	X	
Medical History	X	X					
Medication History	X	X					
Clinical Assessments	X	X			X	X	As needed.
Hematology	X	X			X	X	
Liver Function Tests	X	X			X	X	
Blood Chemistries	X	X			X	X	As needed.

Evaluation	Screening	Entry/Week 0	Weeks			SVR Evaluation Visit (if week 24 visit is missed; can occur up to week 72)	Unplanned Study Visits (see section 6.2.6)
			4	22	24		
			Window \pm 7 days		Window -14/+28 days		
Calculated Creatinine Clearance	X						
INR	X				X	X	As needed.
Pregnancy Testing	X	X			If pregnancy is suspected.		
HBV Panel	X						
CD4+ (if HIV+)	X				X	X	
Plasma HIV-1 RNA (if HIV+)	X				X	X	
Plasma HCV RNA	X				X	X	
Stored Plasma/PBMC/Serum		X			X	X	As needed. (Plasma sample will be stored if blood sample obtained.)
Adherence Assessment			X (via remote contact)		X	X	
Health Outcomes Questionnaire		X			X	X	X
Health Care Utilization Questionnaire		X			X	X	X
Substance Use Questionnaire		X			X	X	

Evaluation	Screening	Entry/Week 0	Weeks			SVR Evaluation Visit (if week 24 visit is missed; can occur up to week 72)	Unplanned Study Visits (see section 6.2.6)
			4	22	24		
			Window \pm 7 days		Window -14/+28 days		
HCV Therapy Dispensed/First Dose Observed		X					
Adherence Education and Counseling		X					
Pregnancy Prevention Counseling	X	X					
Cirrhosis Counseling		X			X	X	
HCV Risk-reduction Counseling		X			X	X	
Locator Information		X	Update information, if needed.				
Remote Contact with Participants Outside of Planned Clinic Visits			X	X (see note in section 6.2.4)			

6.1-2: Schedule of Evaluations: Step 2- Visits Post SVR Evaluation

Evaluation	Weeks			
	42	48	68	72
	Window +28 days			
Calculated FIB-4 Score		X		X
MELD Score		X		X
Calculated CTP Score (if cirrhotic by FIB-4)		X		X
Liver Elastography (see section 6.3.7)		X		X
Clinical Assessments		X		X
Hematology		X		X
Liver Function Tests		X		X

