12.3 General Approach to Costing

The cost/SVR attained will be assessed from two perspectives.

12.3.1 The perspective of the clinic/program/site treating the participant (program perspective). These costs include the cost of staff, laboratory monitoring, and medications involved in delivering HCV treatment to a participant. These costs begin at week 0 and continue through the week 24/SVR evaluation. The program cost perspective is helpful to those who administer a clinic or treatment program who want to understand how MINMON would impact their program budget.

There are two cost components from the program perspective:

1. Cost of HCV medications
2. Cost of planned and unplanned study visit evaluations between week 0 and the week 24/SVR evaluation visit

12.3.2 The healthcare sector perspective—the health sector perspective is broader than the program perspective. It includes the costs of staff, laboratory monitoring and medications between weeks 0 and 24, the cost of healthcare

utilization outside of the study site between weeks 0 and 24, and any changes in utilization that may occur in the future as the result of the participant attaining SVR.

There are four cost components from the healthcare sector perspective:

1. Cost of HCV medications
2. Cost of planned and unplanned study visit evaluations between week 0 and the week 24/SVR evaluation visit
3. Cost of healthcare utilization outside of study sites between week 0 and the week 24/SVR evaluation visit
4. Cost saving (or additional cost) that may accrue because a person attains SVR and subsequently uses fewer (or more) healthcare resources. This cost saving (cost) is defined as the DIFFERENCE in healthcare utilization per month measured at the week 48 visit compared to the week 0 visit. The healthcare utilization questionnaire measures utilization over a 4-week recall period. This is defined as healthcare utilization per month. The difference in healthcare utilization per month between the week 48 assessment and the week 0 assessment is the monthly savings (or cost) attributable to attaining SVR. It will be assumed that the monthly savings (cost) applies to every month between week 24 and week 72.

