12.4.2 Cost of Planned and Unplanned Study Visits

We will consider two components of the cost of a study visit: a) cost of provider time, and b) cost of labs and assessments. Cost of the healthcare visits (Doctor/physician and staff time)—we will use WHO CHOICE estimates of outpatient care delivery costs by country. We will include the week 0 visit (not the screening visit as it is a study procedure with no real-world analogue) and the visit for week 24/SVR evaluation. In addition, we will include any unplanned visits between week 0 and the week 24/SVR evaluation.

We will cost laboratory tests using the national fee schedule for public sector healthcare payers in each country. For example, we will use the Center for Medicare and Medicaid Services (CMS) reimbursement schedule for laboratory test costs in the U.S. and the National Health Laboratory Service schedule for sites in South Africa.

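### The MINMON and standard-of-care costs per SVR are built on different bases: one from study visits as conducted, the other from a care schedule

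*Protocol*

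**What the plan says.** - **What MINMON is charged.** Protocol section 12.3 lists "Cost of planned and unplanned study visit evaluations between week 0 and the week 24/SVR evaluation visit" as a component under both the program and the healthcare-sector perspective. Section 12.6 repeats it as "Cost of all planned and unplanned study visits between weeks 0 and 24/SVR evaluation including staff time and laboratory tests". Section 12.4.2 says what a visit costs: "We will consider two components of the cost of a study visit: a) cost of provider time, and b) cost of labs and assessments".
- **What is left out.** Section 12.4.2 costs the week 0 visit, "not the screening visit as it is a study procedure with no real-world analogue". That is the only exclusion of a study procedure in section 12.
- **What MINMON is.** Section 3.0 opens the strategy with "minimal pre-treatment assessment including confirmation of viremia by HCV RNA and liver disease staging", then full dispensing at entry, no planned on-treatment laboratory tests, no planned visits before the SVR evaluation, and remote contacts at weeks 4 and 22.
- **What else is promised.** Sections 2.2 and 3.0 say that remote-contact costs enter the cost analysis. Section 2.2 says the same of the value of the incentive for attending the SVR visit.
- **The comparator.** Section 12.6 acknowledges that there is no control arm and plans a standard-of-care cost per SVR "based on the cost of laboratory tests and medications and the planned schedule of events for a standard of care treatment course".
- **Status.** Cost per person cured is exploratory (section 1.4.5), though cost per SVR is the primary outcome of section 12. The SAP supplied does not cover the cost analysis.

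**The concern.** A cost per SVR set beside a standard-of-care figure is useful only if both price a way of delivering care. Here the MINMON figure prices a study schedule. It picks up tests that the strategy does not call for and loses some that it does. The protocol recognises the principle when it drops screening for lack of a real-world counterpart, but it does not apply that principle to the week-24 tests. Nor does it ask whether screening contains tests that a real MINMON program would have to pay for.

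The comparator differs again in components, in the source of its schedule, and possibly in its denominator. A program manager who compared the two numbers could not tell how much of the gap came from the strategies and how much from the accounting.

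**Working it through.** **1. Line up what is costed**

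| Item | MINMON, as section 12 reads | Needed by MINMON (section 3.0) | Standard of care |
|---|---|---|---|
| Pre-treatment HCV RNA | Not costed (screening only, Table 6.1-1) | Yes | Yes (Table 2.1-2) |
| Pre-treatment INR | Not costed (screening only) | If FIB-4 indicates cirrhosis | Within baseline labs, not itemised |
| Hematology, liver tests and chemistries before treatment | Costed (repeated at week 0) | Yes, for staging | Yes, as baseline labs |
| Remote contacts, weeks 4 and 22 | Promised in 2.2 and 3.0, not listed in 12.3 or 12.6 | Yes | Not applicable |
| Incentive for SVR visit | Promised in 2.2, not listed in 12.3 or 12.6 | Trial measure, to be costed per 2.2 | Not stated |
| Week-24 HCV RNA | Costed | Yes | Yes, all four countries |
| Week-24 hematology, liver tests, chemistries | Costed | No | Not in Table 2.1-2; the section 2.1 text on Thailand has blood count and chemistry then |
| Week-24 INR, elastography where available | Costed | No | Not in Table 2.1-2 |
| Week-24 CD4+ and HIV-1 RNA, if HIV-positive | Costed | No | Not in Table 2.1-2 |
| Week-24 stored specimens | Unclear whether "cost of labs and assessments" covers them | No | No |
| Staff time | Costed | Yes | Not named in 12.6 |
| Unplanned visits | Costed | Yes, a real cost of the strategy | Only planned events named |
| SVR denominator | Missing = non-SVR (12.3) | n/a | No rate or rule stated |

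Table 6.1-1 has 9 laboratory or procedure rows at week 24/SVR: elastography, hematology, liver tests, chemistries, INR, CD4+, HIV-1 RNA, HCV RNA and stored specimens. Removing HCV RNA leaves 8. Table 2.1-2 has 1 row at 24 weeks.

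**2. How an error in the numerator passes through**

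Let s be the SVR rate with missing counted as failure, and a the share attending the SVR visit. C is the cost per attendee of week-24 tests outside the strategy, P the omitted strategy cost per participant (pre-treatment HCV RNA and INR, remote contacts), and I the omitted incentive per attendee. Then

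change in cost per SVR = [a × (C − I) − P] / s.

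The documents give no value for C, P or I. I assume s from 90% to 98% and a from s to 100%.

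- Each 1.00 of C adds a/s: at the low end s/s = 1.00; at full attendance 1/0.98 = 1.02, 1/0.95 = 1.05 and 1/0.90 = 1.11.
- For tests done only in HIV-positive participants, the cap is 200/400 = 0.50. At that cap and full attendance, each 1.00 adds 0.50/0.98 = 0.51 to 0.50/0.90 = 0.56.
- Each 1.00 of P, omitted for every participant, removes 1/s: 1.02 to 1.11. INR is a strategy test only in those with cirrhosis by FIB-4, at most 80/400 = 20%.

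The MINMON figure is too high only if a × (C − I) exceeds P. The documents do not settle that.

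**3. The denominator**

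Section 2.2 says about 20% of US patients who complete treatment do not return in time for SVR assessment. As an illustration only: if 20% were scored non-SVR in one figure and not in the other, equal costs and equal true cure would still give figures differing by 1/0.80 = 1.25-fold. Late SVR visits count in this trial, so the real effect could be smaller.

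**The case against.** - **Limiting language.** Section 12.3.1 ties program costs to delivering HCV treatment, and in 12.6 the word for all qualifies visits rather than tests. CD4+ and HIV-1 RNA are arguably outside. This makes the text ambiguous, but the components listed in 12.3, 12.4.2 and 12.6 carry no such limit, and no listed sensitivity analysis removes these tests.
- **Bias already acknowledged.** Section 12.3 admits an upward bias from attributing all utilization to HCV medication and from scoring losses as failures, and gives a sensitivity analysis for the latter. That covers loss to follow-up in MINMON. It does not cover week-24 study tests or the comparator's denominator.
- **Unplanned visits.** They are a genuine cost of a strategy without scheduled visits and should stay in.
- **Purpose and weight.** The stated objective in 12.1.1 is the MINMON cost per SVR; the comparator is an addition. The outcome is exploratory, and the SAP leaves other objectives to separate plans that are not available here. All of this stands and limits the weight of the point.

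Three stronger readings are tempting and are not supported.

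- A reader might infer that the plan understates the saving from MINMON. Dropping pre-treatment HCV RNA and INR, and leaving out remote contacts and the incentive, pushes the other way.
- A reader might infer that week-24 safety panels belong to neither strategy. The section 2.1 text on Thailand puts blood count and chemistry at 12 weeks post-treatment for interferon-free regimens.
- A reader might count three on-treatment safety-lab sets in Table 2.1-2 against one charged at week 24 and conclude that a third (1/3 = 33%) of the saving is lost. That is an unweighted count of one component, not a cost. The section 2.1 text on Thailand and Brazil describes fewer routine on-treatment panels than the table, and 12.6 does not name that table as the comparator schedule.

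**Conclusion.** The point holds as a mismatch of bases. As written, section 12 prices MINMON from study visits, including week-24 tests outside the strategy and excluding pre-treatment tests inside it. It prices standard of care from a care schedule with fewer named components and no stated SVR rate or missing-data rule. The exclusion of study-only procedures is applied to screening as a whole and to nothing else.

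The net direction and size are unknown because no unit costs are given. The pass-through factors of 1.00 to 1.11 per unit of week-24 excess, and 1.02 to 1.11 per unit of omitted cost per participant, rest on the assumed SVR range of 90% to 98% and on attendance between the SVR rate and 100%. The primary SVR and safety analyses are unaffected. The point deserves action because the change is cheap and the comparison would otherwise be hard to interpret.

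**What to change.** Revise sections 12.3, 12.4.2 and 12.6, or a separate cost analysis plan, as follows. No test done in the trial changes.

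1. Make the main MINMON analysis cost a prespecified care schedule: pre-treatment HCV RNA and staging labs (INR where section 3.0 calls for it), the entry visit, drug, remote contacts at weeks 4 and 22, unplanned visits and tests ordered for medical need, and the SVR visit with HCV RNA. Include the incentive, as section 2.2 promises.
2. Build the standard-of-care figure country by country from the same components: provider time, labs and drug. Name the schedule used, and include week-24 labs where local care has them, as the section 2.1 text says for Thailand. Section 12.4.2 mentions South African sites, for which Table 2.1-2 has no column, so a source is needed if that country is costed.
3. Report the standard-of-care cost per SVR over a stated range of SVR rates, with missing counted as non-SVR as for MINMON. Apply the existing loss-to-follow-up sensitivity analysis to both figures.
4. Report the as-conducted cost of all study evaluations as a sensitivity analysis, and say whether it includes stored specimens.

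The cost is wording plus slightly more analysis on an exploratory outcome. The schedule identifies the tests item by item, and section 3.0 already has staff time for remote contacts documented.

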13.0 DATA COLLECTION AND MONITORING

13.1 Records to Be Kept

eCRFs will be made available to sites for data entry. Participants must not be identified by name on any data submitted to the DMC. Participants will be identified by the patient identification number (PID) and study identification number (SID) provided by the ACTG DMC upon registration.

13.2 Role of Data Management

- 13.2.1 Instructions concerning entering study data on eCRFs will be provided by the ACTG DMC. Each CRS is responsible for keying the data in a timely fashion.

- 13.2.2 It is the responsibility of the ACTG DMC to assure the quality of computerized data for each ACTG study. This role extends from protocol development to generation of the final study databases.

13.3 Clinical Site Monitoring and Record Availability

- 13.3.1 Site monitors under contract to the NIAID will visit participating clinical research sites to review the individual participant records, including consent forms, eCRFs, supporting data, laboratory specimen records, and medical records (physicians' progress notes, nurses' notes, individuals' hospital charts), to ensure protection of study participants, compliance with the protocol, and the accuracy and completeness of records. The monitors also will inspect sites' regulatory files to ensure that regulatory requirements are being followed and sites' pharmacies to review product storage and management.
- 13.3.2 The site investigator will make study documents (e.g., consent forms, drug distribution forms, eCRFs) and pertinent hospital or clinic records readily available for inspection by the local IRB, the site monitors, the FDA, the NIAID, the OHRP, the industry supporter and local, US, and international regulatory entities for confirmation of the study data.

14.0 PARTICIPANTS

14.1 Institutional Review Board (IRB) Review and Informed Consent

This protocol and the informed consent document ([Appendix I](#)) and any subsequent modifications will be reviewed and approved by the IRB or ethics committee responsible for oversight of the study. A signed consent form will be obtained from the participant (or legal guardian, or person with power of attorney for participants who cannot consent for themselves. The consent form will describe the purpose of the study, the procedures to be followed, and the risks and benefits of participation. A copy of the consent form will be given to the participant, or legal guardian and this fact will be documented in the participant's record.

14.2 Participant Confidentiality

All laboratory specimens, evaluation forms, reports, and other records that leave the site will be identified by coded number only to maintain participant confidentiality. All records will be kept locked. All computer entry and networking programs will be done with coded numbers only. Clinical information will not be released without written permission of the participant, except as necessary for monitoring by the ACTG, IRB/EC, FDA, NIAID, OHRP, other local, US, and international regulatory entities as part of their duties, or the industry supporter(s) or designee.

14.3 Study Discontinuation

The study may be discontinued at any time by the ACTG, IRB/EC, FDA, NIAID, OHRP, other country-specific government agencies as part of their duties to ensure that research participants are protected, or the industry supporter.

15.0 PUBLICATION OF RESEARCH FINDINGS

Publication of the results of this trial will be governed by ACTG policies. Any presentation, abstract, or manuscript will be made available for review by the industry supporter prior to submission.

16.0 BIOHAZARD CONTAINMENT

As the transmission of HIV and other blood-borne pathogens can occur through contact with contaminated needles, blood, and blood products, appropriate blood and secretion precautions will be employed by all personnel in the drawing of blood, and shipping and handling of all specimens for this study, as currently recommended by the Centers for Disease Control and Prevention and the National Institutes of Health.

All dangerous goods and materials, including diagnostic specimens and infectious substances, must be transported using packaging mandated by CFR 42 Part 72. Please refer to instructions detailed in the International Air Transport Association (IATA) Dangerous Goods Regulations.

